## e. Statistical Design and Power

**1. Power and Sample Size Determination:** Power to detect changes in PCr:tP between groups is our primary determinant of sample size in the R61 phase because of the centrality of spectroscopic findings in our hypotheses. In another study, after 8-weeks of oralCr, adult female methamphetamine users had significantly increased PCr levels with a standardized effect size of

0.920. In an open-label study in depressed adolescents. PCr levels following Cr administration increased by 6.2%+ 9.6%. In a dose-finding study of Cr compared to placebo, the effect size for differences in PCr levels between the group receiving 4 grams of Cr daily compared to placebo was 0.7. We hypothesize that supplementation with Cr with or without 5-HTP will increase frontal cortical PCr levels. P-MRS neuroimaging will be performed at baseline, and repeated after 8 weeks of treatment with Cr + placebo, 5-HTP + placebo, or 5-HTP + Cr. To address our first hypothesis, a population-averaged generalized estimating equation (GEE) regression model is used for group comparison of the  $\Delta PCr$  (PCrWEEK 8 - PCrBASELINE) associated with Cr + placebo, 5-HTP + placebo, or 5-HTP + Cr. We will control for age, gender, and tissue partial volume effects (i.e., gray matter, white matter and cerebrospinal fluid) for in vivo phosphorus metabolite measurements made at two time points. The GEE for each subject, i has the form Yi(t)=Xi  $\beta$  +  $\epsilon_i$ , where Yi and Xi represent measured metabolite (PCr or  $\beta$ -NTP) levels and design matrix of covariates, respectively. The error term follows a multivariate normal distribution:  $\varepsilon_i \sim N(0, V_i)$ , where Vi is the variance of metabolite levels. We assume that measures taken closer to each other in time are more highly correlated than those taken further apart. Therefore, the first-order autoregressive structure, AR(1) is assumed such as  $cov[\varepsilon_i(t), \varepsilon_j(t')] = \rho^{|t-1|}$ tVi to model the dependence of the correlation on repeated measures from the same participant, where t is time variable and p is the correlation coefficient between the clinical symptom measures of two successive assessments. Assuming  $\rho = 0.30$ , expected MDES = 5% across the groups, and harmonic mean SD = 10%, respectively, a sample size of 60 participants (15 per group; 4 aroups) and 2 neuroimaging time points per participant has >80% power using the AR (1) GEE model at the 0.05 alpha level. In our open-label study, we experienced ~20% participant attrition. Imputation of missing data cannot be utilized for neuroimaging data. Therefore, anticipating a 20% attrition rate, we propose a target enrollment of 75 participants for the R61 phase.

2. Analysis of P-MRS Data: To analyze study data, a raw Hamming filter will be applied before performing 2D fast Fourier transformation, and each free induction decay (FID) will be linebroadened with 10 Hz of apodization. After Fourier transformation and frequency shift correction. zero-/first-order phase correction and baseline correction with polynomial interpolation will be applied. Spatial filtering with a Hamming window function will be implemented to reduce signal contamination from neighboring voxels. The preprocessed P-MRSI data will be fitted using jMRUI software with the Advanced Method for Accurate, Robust and Efficient Spectral (AMARES) fitting algorithm. Metabolites of interest include PCr, β-NTP, tP, and their ratios. From registered anatomical images, tissue segmentation will be performed using FSL (FMRIB's Software Library) software so that cerebrospinal fluid (CSF)-corrected metabolite concentrations as well as gray matter percentage in each voxel can be used as covariates in the analysis. Generalized estimating equations regression modeling will be used to evaluate group differences in metabolite levels controlling for age, sex, education level, and tissue partial volume effects (i.e. gray matter, white matter, CSF). Subjects with MDD will be compared to HCs at baseline and at follow-up. Sub-group analyses by gender will be included given evidence that Cr has been proposed as especially effective in women. Fisher's exact test will be used to compare groups on categorical variables.

**3. Analysis of Resting State Data:** As is seen in the small cohort of pilot data, we anticipate treatment groups to demonstrate increased global connectivity of the subgenual ACC after treatment, among other changes. A recent analysis determined that we can achieve single subject reproducibility of FC metrics of 0.16 Fisher-transformed correlation units. If we conservatively set the effect size at 8% and SD at 9% of mean, a sample size of 60 depressed subjects would achieve >90% power to detect significant treatment effects with the repeated measures design compared to baseline. For FC analyses, 361 regions of interest (ROIs) comprising a parcellation of cortical gray matter will be compared between placebo and active treatment subjects. We

will conduct a second level of analysis using eight networks delineated as follows and derived from Gordon *et al.*: auditory, salience, frontoparietal, default, dorsal attention, ventral attention, sensorimotor, and visual. Two levels of analysis will be performed to balance multiple comparisons and granularity of spatial information. For each pair of 8 networks, mean BOLD time series will be extracted across the entire network and Fisher-transformed correlation coefficients will be calculated. An acceptable false discovery rate (q < .05) over all pairs of networks will be assumed to denote significant partial correlation with diagnosis. To evaluate which connections are anticorrelated, we will use an independent dataset for an unbiased estimate obtained from the S1200 Release of the Human Connectome Project (HCP) dataset. Group-wise ANOVA will be performed with false discovery rate correction for multiple comparisons across 361 x 361 connections tested for treatment group differences in FC before and after treatment compared to placebo group. Sub-group analyses by gender will be included given evidence that Cr has been proposed as especially effective in women. Subjects with MDD will be compared to HCs at baseline and at follow-up.

**4. Analysis of 5-HT Levels:** There is limited data available regarding the effect of twice-daily oral 5-HTP supplementation on whole blood 5-HT levels in subjects with MDD taking ADs. Estimates of whole blood (platelet) serotonin levels in MDD vary widely, including values from  $119 \pm 52.9$  ng/ml (n=30) to  $169.5 \pm 74.5$  ng/ml (n=29) to  $203.2 \pm 59.3$  ng/ml (n=25), suggesting that whole blood 5-HT levels average roughly  $161 \pm 62$  ng/ml in subjects with MDD. A sample of 60 subjects with MDD allocated 1:1 between 5-HTP (5-HTP+Cr and 5-HTP+placebo) and placebo (Cr+placebo and placebo+placebo) would have, in a t-test of means, >70% power to detect an effect size of 0.8. This effect size would be equivalent to an increase in average 5-HT levels to roughly those seen in non-depressed subjects. Although this is a relatively large effect size, it is consistent with findings related to the effect of oral tryptophan supplementation (at 50mg/kg/day in non-depressed men) which found an estimated effect size of 1.1. This analysis assumes that creatine supplementation will not independently affect circulating serotonin levels, though there is no data regarding this to our knowledge. 5-HT levels will be analyzed using linear mixed models with repeated (before and after) measures, controlling for gender, age, group allocation, antidepressant use, oxygen saturation, and other confounds.

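### PCr is compared as week 8 minus baseline without baseline adjustment, giving 2/(1+ρ) times the variance of an adjusted contrast: 54% more at the plan's ρ = 0.30, 5% to 82% more for ρ from 0.9 to 0.1

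*Combined protocol and SAP*

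**What the plan says.** Section e.1 makes spectroscopy the basis of the sample size: "Power to detect changes in PCr:tP between groups is our primary determinant of sample size in the R61 phase". For the first hypothesis it then says that "a population-averaged generalized estimating equation (GEE) regression model is used for group comparison of the" change in PCr between the baseline and week-8 scans.

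The model is written on metabolite levels at the two time points, with AR(1) correlation within participant. The design matrix is described only as containing covariates.

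Two covariate lists are given:
- e.1: "We will control for age, gender, and tissue partial volume effects".
- e.2 (Analysis of 31P-MRS Data): "controlling for age, sex, education level, and tissue partial volume effects".

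Neither list contains baseline PCr, and no text sets the arms' baseline means equal.

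The power statement takes ρ = 0.30 with "expected MDES = 5% across the groups, and harmonic mean SD = 10%, respectively", 15 participants in each of four arms and alpha 0.05, and reports power above 80%. The plan says that ρ "is the correlation coefficient between the clinical symptom measures of two successive assessments", although it is applied to PCr.

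**The concern.** A change score subtracts the whole baseline value, whatever its correlation with the follow-up. If the correlation is modest, most of what is subtracted is noise. Regression on baseline subtracts only the predictable part, so in large samples its variance is never higher, and it is strictly lower for any ρ below 1.

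Both contrasts are unbiased under randomisation, so validity is not at stake. The question is how much information is lost in a trial with 15 participants per arm, where the plan itself rules out imputing missing imaging data. The baseline scan that would recover the loss is already scheduled for every participant.

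**Working it through.** **Inputs.** From e.1: difference 5%, SD 10%, ρ = 0.30, 15 per arm, four arms, two scans, alpha 0.05. My assumptions:
- two-sided testing;
- equal variance at the two scans;
- creatine arms against non-creatine arms (30 v 30) with no creatine by 5-HTP interaction, because the plan does not name the contrast behind its power figure.

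The plan does not say whether the 10% is the SD of one level or of the change, so both are carried.

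**Step 1: the plan's own figure.** If 10% is the SD of change, SE = 10 × √(2/30) = 2.582 and 5/2.582 = 1.94; noncentral-t power is 48%. If 10% is the SD of a level, the change SD is 10 × √(2 × 0.70) = 11.83, SE = 3.055, and power is 36%. The stated figure of more than 80% is not reproduced by any two-group contrast tried (20% to 67% two-sided, at most 78% one-sided). That is a separate problem; it is noted so that the gains below are not misread.

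**Step 2: the levels model is the change score.** With group, time and group-by-time terms and complete pairs, the generalised least squares variance of the group-by-time coefficient (30 v 30, level SD 10, ρ = 0.30) is 9.33, which equals 3.055². With one common baseline mean it is 6.07, which equals 2.463², the baseline-adjusted variance. Specifying AR(1) does not by itself recover the difference.

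**Step 3: variance ratio.** With level variance σ², the change has variance 2σ²(1−ρ) and the adjusted outcome σ²(1−ρ²). The ratio is 2(1−ρ)/(1−ρ²) = 2/(1+ρ). Standard errors below are for 30 v 30 with a level SD of 10.

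| ρ | 2/(1+ρ) | Excess variance | SE, change | SE, adjusted |
|---|---|---|---|---|
| 0.1 | 1.818 | 82% | 3.464 | 2.569 |
| 0.3 | 1.538 | 54% | 3.055 | 2.463 |
| 0.5 | 1.333 | 33% | 2.582 | 2.236 |
| 0.7 | 1.176 | 18% | 2.000 | 1.844 |
| 0.9 | 1.053 | 5% | 1.155 | 1.125 |

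At ρ = 0.30 the reduction in SE is 1 − 2.463/3.055 = 19%. If 10% is the SD of change, the adjusted SD is 10 × √(1.30/2) = 8.06 and the SE falls from 2.582 to 2.082, again 19%.

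The change score is noisier than ignoring the baseline scan when 2(1−ρ) > 1, that is when ρ < 0.5. At the plan's ρ its variance is 1.40σ², against σ² for week 8 alone.

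**Step 4: power for a 5% difference, change v adjusted** (noncentral t, one degree of freedom spent on baseline).

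| Contrast | ρ | 10% is SD of a level | 10% is SD of change |
|---|---|---|---|
| 30 v 30 | 0.3 | 36% v 51% | 48% v 66% |
| 30 v 30 | 0.5 | 48% v 59% | 48% v 59% |
| 30 v 30 | 0.7 | 69% v 76% | 48% v 54% |
| 15 v 15 | 0.3 | 20% v 28% | 26% v 37% |

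**Step 5: small-sample check.** A simulation of 10,000 trials with 15 per arm and ρ = 0.30 used t-based linear models. Five extra covariates, assumed unrelated to outcome, were included (age, sex, education, gray and white matter; CSF is redundant if the fractions sum to one). The variance ratio was 1.50. Power was 34% v 48% (level SD) and 44% v 60% (change SD). Rejection under the null was 5.0% v 5.2%. The gain survives the planned covariates and the lost degree of freedom.

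**The case against.** The best defence is that the model is written on levels, so baseline PCr is a response and would not appear in a covariate list even if the baseline means were constrained. Section e.2 also speaks of differences in metabolite levels, not change. It is true that the covariate lists alone do not settle the matter and that the loss depends on the arms having separate baseline means. But e.1 names the change as the quantity compared, and nothing states a constraint. If one was intended, writing it down resolves the point.

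Second, 54% rests on a ρ whose relevance to PCr is doubtful. This stands: the range is the firmer statement, and at ρ = 0.9 the gain is negligible.

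Third, the absolute standard errors depend on what the 10% measures. This also stands. The model's variance term refers to metabolite levels, but e.1 cites an open-label PCr increase of 6.2% with what appears to be an SD of change of 9.6%. The relative saving is the same on either reading.

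Finally, an unbiased contrast with correct type I error is acceptable in a proof-of-concept study. That limits the severity. It is no reason to leave collected information unused.

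**Conclusion.** The concern holds. As written, the PCr comparison is a raw change contrast with 2/(1+ρ) times the variance of a baseline-adjusted one: 54% excess at the plan's ρ = 0.30, between 5% and 82% over ρ = 0.9 to 0.1. This rests on equal variance at both scans, randomised arms, complete pairs, and a design matrix with separate baseline means for each arm. Confidence is medium because that matrix is not stated and no PCr or PCr:tP test-retest correlation is given.

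It is an avoidable loss of precision, not a bias, and it should be corrected. Correcting it does not substantiate the power claim at ρ = 0.30.

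**What to change.** Keep the covariates already listed and choose one of:

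- (a) model week-8 PCr with baseline PCr added as a covariate; or
- (b) keep the two-time-point model and constrain the baseline means of the randomised arms to be equal. The constraint must not extend to the healthy controls mentioned in e.2, who are not randomised.

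Write out the design matrix. Under (a), also say which scan's tissue fractions enter the model. Treat β-NTP the same way, and PCr:tP if that ratio is the outcome tested. The plan names no standard-error estimator; if GEE with a sandwich variance is used at 15 per arm, specify a small-sample correction and a t reference. The simulation above did not test that estimator.

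The cost is SAP wording and one degree of freedom. No planned covariate is dropped and no new data are needed.

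### The metabolite GEE with about 15 participants per arm has no stated variance estimator, reference distribution, small-sample correction or contrast; run in its usual uncorrected form it exceeds the 5% level

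*Combined protocol and SAP*

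**What the plan says.** Section e, Statistical Design and Power, item 1 (Power and Sample Size Determination) gives this comparison its weight: "Power to detect changes in PCr:tP between groups is our primary determinant of sample size". The same item sets out the model for the change in PCr from baseline to week 8: "a population-averaged generalized estimating equation (GEE) regression model is used for group comparison". It adjusts for age, gender and tissue fractions, uses an AR(1) correlation structure, and states that "The error term follows a multivariate normal distribution". The sample size is 60, or 15 per group in four groups, with "2 neuroimaging time points per participant". This is said to be a design that "has >80% power using the AR (1) GEE model at the 0.05 alpha level". On losses: "anticipating a 20% attrition rate, we propose a target enrollment of 75 participants for the R61 phase". Missing scans are not to be imputed.

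Item 2 (Analysis of 31P-MRS Data) repeats the choice: "Generalized estimating equations regression modeling will be used to evaluate group differences in metabolite levels". It adds education to the covariates and plans sub-group analyses by gender.

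Neither item says whether standard errors are sandwich or model-based, whether tests refer to z/chi-square or t/F, whether a small-sample correction applies, or which contrast or joint test decides the hypothesis. The hypothesis as worded is that creatine, with or without 5-HTP, raises frontal PCr. That points to a pooled creatine against no-creatine contrast.

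**The concern.** GEE is usually reported with the empirical (sandwich) variance and a Wald test against a normal or chi-square reference. That procedure relies on a large number of independent participants. Here there are about 60, in four arms, with several covariates. Two things then go wrong in the same direction. The sandwich is built from fitted residuals, which are smaller on average than the true errors, so the variance is biased low. The z/chi-square reference also makes no allowance for having estimated that variance.

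The consequence would be a test of the first hypothesis that rejects more often than the stated 5%, with intervals that cover less than 95%. Because the estimator is not named, the choice between a well-calibrated and a miscalibrated test would also remain open at analysis.

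**Working it through.** **The plan's own figures.** Enrolment reproduces: 60 / (1 − 0.20) = 75. The power above 80% does not reproduce for a 5% difference with SD 10%. Using power ≈ Φ(δ/SE − 1.96):
- 15 v 15: SE = 10·√(2/15) = 3.65, 5/3.65 = 1.37, power 28%.
- 30 v 30: SE = 10·√(2/30) = 2.58, 5/2.58 = 1.94, power 49%.
- With the change-score SD, 10·√(2(1 − 0.30)) = 11.83: 21% and 37%.

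That is a separate matter and nothing below depends on it.

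**Inputs.** From item 1: four arms, 15 per arm, two scans, SD 10%, ρ = 0.30, normal errors, alpha 0.05; adjustment for age, sex and two tissue fractions. Assumed: two-sided testing and equal variances across arms. Sensitivity: 12 per arm (60 × 0.8 / 4, if 60 are randomised before loss) and 19 per arm (75 / 4 = 18.75, no loss). With only two scans, AR(1) and exchangeable correlation are the same structure.

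**Hand check (change score, no covariates).** With n per arm, the uncorrected sandwich estimates each arm's variance with divisor n instead of n − 1, so it is low by (n − 1)/n = 14/15 = 0.933. The standard error is low by √0.933 = 0.966. Comparing with 1.96 is then the same as comparing an exact t statistic with 1.96 × 0.966 = 1.893:
- one arm v placebo: P(|t₂₈| > 1.893) = 6.9%
- pooled creatine v no creatine: P(|t₅₆| > 1.893) = 6.3%

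Simulation of this case gave 6.8% and 6.3%.

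**Simulation under no effect.** 20,000 trials per setting; Monte Carlo standard error about 0.2 points. The sandwich is V = A⁻¹(Σ Xᵢ′Vᵢ⁻¹ rᵢrᵢ′ Vᵢ⁻¹Xᵢ)A⁻¹ with A = Σ Xᵢ′Vᵢ⁻¹Xᵢ. Mancl-DeRouen replaces rᵢ by (I − Hᵢ)⁻¹rᵢ; t/F tests use n − p denominator degrees of freedom. Rejection rates at nominal 5%, 15 per arm, covariate-adjusted:

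| Test | Two-scan model | Change score |
|---|---|---|
| One arm v placebo, sandwich, z | 6.9% | 7.8% |
| Pooled creatine v no creatine, sandwich, z | 6.3% | 7.7% |
| Joint 3-df, sandwich, chi-square | 9.3% | 11.7% |
| One arm v placebo, model-based, z / t | 5.9% / 5.1% | 5.4% / 4.9% |
| One arm v placebo, Mancl-DeRouen, t | 4.5% | 3.9% |
| Pooled creatine v no creatine, Mancl-DeRouen, t | 4.2% | 3.6% |
| Joint 3-df, Mancl-DeRouen, F | 5.3% | 4.3% |

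A separate run of the adjusted two-scan model gave 6.6%, 6.7% and 9.5% for the three uncorrected tests, and 5.0-5.9% with model-based standard errors.

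**Sensitivity to n (two-scan, adjusted, uncorrected).** For 12 / 15 / 19 per arm: one arm v placebo 7.2% / 6.9% / 6.7%; pooled creatine 6.6% / 6.3% / 6.3%; joint 10.7% / 9.3% / 8.5%.

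**Which part matters.** In the two-scan model with 15 per arm, changing only the reference from z to t moves the single contrast from 6.9% to 6.2%. Correcting only the variance moves it to 5.0%. The bias in the sandwich is the larger part, so a t reference alone is not enough.

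**The case against.** The strongest objection is that the documents name neither a sandwich variance nor a Wald test. Item 1 writes a parametric model with normal errors and an explicit covariance, which fits model-based standard errors at least as well, and those run at about 5-6%. This stands. A reader might infer that the planned test does run at 7-11%; the documents do not support that, and the inflation has to be stated as conditional.

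The upper end of that range also belongs to a joint 3-df test, which the plan does not name. The contrast nearest the stated hypothesis, pooled creatine, is at about 6-7% in the two-scan model. The change-score figures are higher, but one value per participant leaves no within-person correlation to model, so they fit the AR(1) description less well. Item 1 names both the change and the two-scan structure, so both readings are open.

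Nor does every empirical-variance test fail. A generalised score test on the adjusted change score with 15 per arm ran at 6.0% for a single contrast and 5.5% for the joint test.

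A reader might also infer that GEE should be abandoned because normal errors are assumed anyway. That goes too far. If one active arm had twice the SD of the others (an assumption), an ordinary pooled-variance linear model ran at 9.7% for that arm against placebo. The uncorrected sandwich ran at 8.7% and Mancl-DeRouen at 4.5%. With both creatine arms at 1.5 times the SD, the linear model held at 4.8%. Robust variance therefore has a purpose here.

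Finally, this is a single-centre proof-of-concept study, and 6-7% instead of 5% is a modest error. That limits the weight of the point. It does not remove it, because the usual way of running the named method misses the stated alpha and the remedy is simple.

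**Conclusion.** The point holds in conditional form. The plan commits the metabolite comparisons to GEE with about 15 per arm and leaves open the choices that decide whether the 0.05 level is kept. Under the uncorrected sandwich with a Wald z/chi-square test:
- a single or pooled creatine contrast runs at about 6-7% in the adjusted two-scan model and 7-8% on the change score;
- a joint 3-df test runs at about 9-10% and 12% respectively.

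A nominal 95% interval for a single or pooled contrast then covers about 93-94% in the two-scan model (100 − 6.9 = 93.1; 100 − 6.3 = 93.7). With model-based variance the single-contrast rate is about 5-6%.

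These figures assume normal errors, ρ = 0.30, equal arm variances, two-sided tests and 15 analysed per arm. The rates of 12 and 19 per arm only bracket the unclear number randomised; the plan's stated analysis number is 15. The gender sub-groups would have fewer participants still, but the sex split is not given, so no figure is attached to them here.

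**What to change.** In Section e, items 1 and 2, add one statement of how inference is done. Either of these would do:

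- **Keep GEE:** all tests and confidence intervals use a bias-corrected sandwich variance (for example Mancl-DeRouen) with a t or F reference.
- **Use a normal-theory model:** a mixed model for the two scans with Kenward-Roger degrees of freedom, or ANCOVA of the week-8 value, with t/F tests. If this is chosen, state whether arm variances are assumed equal, since that is where a robust variance has the advantage.

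In the same place, name the contrast for the first hypothesis: creatine (both arms) against no creatine (both arms). This also settles a loose end in item 1, where the description of the comparison lists three arms while the sample size counts four. Apply the same inference rule to the gender sub-group analyses.

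The cost is a few lines of text and a different procedure option, with no new data, visits or participants. Intervals become slightly wider and the stated power slightly lower. On the pooled contrast, the corrected test is somewhat conservative (4.2% in the two-scan model, 3.6% on the change score).

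### The correlation in the PCr power calculation is defined for symptom scores and has no PCr source, the 10% SD is not identified, and no reading of these inputs gives the stated >80% power for a 5-point difference in PCr change between groups

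*Combined protocol and SAP*

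**What the plan says.** All of the following is in the combined protocol and SAP, section e. Statistical Design and Power, item 1 (Power and Sample Size Determination).

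- **Endpoint.** Power to detect change in PCr:tP between groups is named as the main determinant of sample size. For the first hypothesis, a "generalized estimating equation (GEE) regression model is used for group comparison of the" week 8 minus baseline change in PCr.
- **Model.** The outcome is the measured metabolite level (PCr or beta-NTP), and V_i "is the variance of metabolite levels". The working correlation is AR(1).
- **Correlation.** The parameter is defined as follows: "p is the correlation coefficient between the clinical symptom measures of two successive assessments" (the extracted p is rho). It is set to 0.30 with no reference.
- **Effect and SD.** "expected MDES = 5% across the groups, and harmonic mean SD = 10%, respectively". The text does not say whether the SD is of PCr levels or of PCr change.
- **Claim.** "a sample size of 60 participants (15 per group", four groups, two scans each) is said to give more than 80% power at the 0.05 level. Neither the contrast nor the sidedness behind that figure is stated.
- **Cited PCr data.** "In an open-label study in depressed adolescents", "PCr levels following Cr administration increased by 6.2%+ 9.6"%. The spread is not labelled as an SD or a standard error.

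**The concern.** For a comparison of change between two scans, the relevant correlation is that between a participant's baseline PCr and the same participant's week-8 PCr. Together with the SD of levels, it fixes the SD of change and therefore the power. A correlation between symptom ratings does not tell us this, and no symptom score enters the model. With no PCr source for 0.30, a reader cannot judge whether the value suits the endpoint.

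The unidentified 10% adds to the difficulty. The correlation is either essential (SD of levels) or unnecessary (SD of change), and the paragraph does not show which. The sample size of 60, and the enrolment target of 75 derived from it, rest on this one paragraph. If its inputs do not deliver the stated power, a null PCr result could not be read as evidence of no effect of the size planned for.

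**Working it through.** **Inputs, all from item 1:** difference 5 percentage points; SD 10%; rho 0.30; alpha 0.05; 15 per group, two scans; cited spread of PCr change 9.6%. **Assumptions made here:** two-sided test; the 9.6% is an SD; all 60 participants have both scans. Two contrasts are shown: 15 v 15 (one group against another) and 30 v 30 (both creatine groups against both groups without creatine).

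**Step 1. Trying to reproduce >80%.** With two scans, AR(1) has a single correlation, so

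SD of change = SD × sqrt(2(1 − rho)) = 10 × sqrt(2 × 0.70) = 10 × sqrt(1.4) = 11.83%.

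Power comes from the noncentral t distribution with noncentrality 5 / (SD of change × sqrt(2/n)), where n is the number per side.

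- 30 v 30: 5 / (11.83 × 0.2582) = 1.64 on 58 df, power 36%.
- 15 v 15: 5 / (11.83 × 0.3651) = 1.16 on 28 df, power 20%.

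The stated figure does not reproduce.

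**Step 2. The 10% read as an SD of change.** Rho then drops out.

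- 30 v 30: 5 / (10 × 0.2582) = 1.94, power 48%.
- 15 v 15: 5 / (10 × 0.3651) = 1.37, power 26%.

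**Step 3. The cited 9.6% used as the SD of change.**

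- Implied rho at a level SD of 10%: 1 − 9.6² / (2 × 10²) = 1 − 92.16/200 = 0.54.
- 30 v 30: 5 / (9.6 × 0.2582) = 2.02, power 51%.
- 15 v 15: 5 / (9.6 × 0.3651) = 1.43, power 28%.

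**Step 4. Power over an assumed range of rho (level SD 10%).**

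| rho | SD of change | 15 v 15 | 30 v 30 |
|---|---|---|---|
| 0.10 | 13.42% | 17% | 30% |
| 0.30 | 11.83% | 20% | 36% |
| 0.54 | 9.60% | 28% | 51% |
| 0.70 | 7.75% | 40% | 69% |
| 0.80 | 6.32% | 55% | 85% |
| 0.90 | 4.47% | 84% | 99% |

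Power of 80% needs rho of about 0.77 for 30 v 30 and about 0.89 for 15 v 15.

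**Step 5. Could another reading explain >80%?**

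- One-sided test, 30 v 30: 49% (SD of change 11.83%), 61% (10%), 64% (9.6%).
- Baseline-adjusted week-8 comparison, SD = 10 × sqrt(1 − 0.30²) = 9.54%: 52% for 30 v 30 and 28% for 15 v 15, two-sided.
- Mean of the two scans instead of their difference, SD = 10 × sqrt(1.3/2) = 8.06%, 30 v 30: 66% two-sided, 77% one-sided.
- Four-group F test with means spread over 5 points and SD of change 11.83%: 14% to 23%, depending on the pattern of means.

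Calculations that do pass 80% answer a different question or abandon the stated inputs:

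- A pooled pre-post test with no group comparison gives 81% (n = 45) or 90% (n = 60) at rho 0.30, by the normal approximation.
- Taking 5/10 = 0.5 as Cohen's f in a four-group F test gives 90% with SD 10%. That requires group means with an SD of 5 points, for example 0, 0, 10, 10, which is a 10-point difference. With the SD of change at rho 0.30 it gives 76%.
- Averaging the two scans as if independent, 30 v 30, one-sided, gives 86%. That sets rho to 0 and is not a comparison of change.

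**The case against.** The strongest reply is that this is a slip of wording. The variance in the model is stated to be that of metabolite levels, and the 5% and 10% are given for the PCr comparison. The symptom-score phrase may be carried-over text, and 0.30 may have been meant for PCr from the start. This stands in part. A reader might infer that the power rests on the variance of another measure, or that it says nothing about PCr at any sample size. The documents do not support either reading: only the correlation is mislabelled, and nothing shows that 0.30 was estimated from symptom scores.

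A second reply is that the cited 9.6% does not contradict the plan, and this too stands in part. It would be tempting to call 9.6% the plan's own SD of change. It is background from a single external open-label study in adolescents, whereas this trial enrols adults aged 25 to 40, and its spread is unlabelled. The gap between 11.8% and 9.6% exists only if the 10% is an SD of levels. If it is an SD of change, the two figures are close.

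A third reply is that 0.30 is conservative. For a change contrast, moving from 0.30 to 0.54 raises 30 v 30 power from 36% to 51%. That is correct, so the mislabelled correlation cannot be said to have inflated the power. It does not rescue the claim, because both values leave power well below 80%.

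On the harmonic mean SD, a harmonic mean never exceeds the root-mean-square that governs a contrast, so it can understate the variance. The two are equal when group SDs are equal, and no group SDs are given, so no size can be attached to this.

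**Conclusion.** The point holds in a limited form. The correlation entering the PCr power calculation is defined for a measure that is not in the model, its value has no PCr source, and the plan does not say what its 10% SD describes. The stated power of more than 80% does not follow from the inputs for a 5-point difference in PCr change between groups: it is 36% to 51% for 30 v 30 and 20% to 28% for 15 v 15.

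These figures assume a two-sided 0.05 test, complete scans in all 60 participants, equal group SDs, and no gain from the planned adjustment for age, gender and tissue fractions, which the documents do not quantify. They could be overturned by a documented repeat-scan PCr correlation of about 0.77 or more (30 v 30), or by a contrast or effect definition that the plan does not now state. The correction is worth making because the whole sample-size justification depends on this paragraph.

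**What to change.** In section e. Statistical Design and Power, item 1:

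1. Define rho as the within-participant correlation of PCr (or PCr:tP, whichever is primary) between the baseline and week-8 scans. Remove the reference to symptom measures and give the source of the value.
2. State whether the 10% is an SD of levels or of change, and use a pooled (root-mean-square) SD in place of the harmonic mean. If it is an SD of change, drop rho from the power statement.
3. Name the contrast that the power refers to (one group against another, pooled creatine against no creatine, or the four-group test) and its sidedness.
4. Replace the >80% claim with the power recomputed from these inputs, shown over a range of rho. The 9.6% can serve as one sensitivity value, labelled with its source, but should not be adopted as the planning SD without further support.

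The cost is protocol and SAP wording and one recalculation; no extra participants or procedures are needed. The downside is that, on the inputs now given, the printed power becomes less favourable.
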